### **2.2 Rationale for the study design**

This is a multi-center, open-label, phase IV study to better characterize the long-term safety of everolimus in patients being treated in a current Novartis-sponsored, OGD&GMA study and who are benefiting from treatment with everolimus. Patients may be allowed to continue combination therapy with Sandostatin LAR® Depot if they are currently receiving this combination therapy on the parent protocol and at the discretion of the investigator.

This study will not include a screening phase as patients will transfer directly from the parent study and will commence with everolimus as soon as they are consented and meet the inclusion criteria of the roll-over protocol.

### **2.3 Rationale for dose and regimen selection**

Everolimus will be provided as 2.5 mg, 5 mg or 10 mg tablets. At the time of transition to the roll-over study, the starting dose of everolimus should be the same as the last dose that was

given in the parent study. Dose modification thereafter may be done at the discretion of the investigator based upon what is in the patient's best interest.

The roll-over protocol is designed to provide continued treatment with everolimus monotherapy to patients. If patients are receiving treatment of everolimus in combination with other approved therapies, they can participate in the roll-over study but it is not intended for combination with unapproved or experimental treatments. Therefore, for patients receiving everolimus in combination with Sandostatin LAR® Depot, Sandostatin LAR® Depot will be provided by Novartis or by the investigational site considering local regulations. At the time of transition to the roll-over study, the starting dose of Sandostatin LAR® Depot should be the same as the last dose that was given in the parent study.

## **2.4 Rationale for choice of combination drugs**

Patients may be allowed to continue combination therapy with everolimus and Sandostatin LAR® Depot at the discretion of the investigator if they are currently receiving this combination therapy on the parent protocol and are deriving benefit as defined in the criteria of the parent protocol.

## **2.5 Rationale for choice of comparators drugs**

Not applicable.

## **2.6 Risks & Benefits**

### **Postmenopausal women with hormone receptor-positive advanced breast cancer in combination with aromatase inhibitors, after prior endocrine therapy**

Overall, everolimus + exemestane is considered to have a positive benefit-risk profile for postmenopausal women with hormone receptor-positive advanced breast cancer in combination with an aromatase inhibitor, after prior endocrine therapy; the benefits of therapy with everolimus + exemestane outweigh any potential risks.

### **Advanced neuroendocrine tumors of pancreatic origin**

Everolimus has a positive benefit-risk profile for patients with advanced pancreatic neuroendocrine tumors (pNET). Prior study results support the use of everolimus for the treatment of patients with advanced pNET. Results provided evidence that everolimus, in combination with octreotide depot, improved PFS in patients with advanced carcinoid tumors. The primary endpoint of the study was not met. More data is needed to better assess the benefit-risk of everolimus in this patient population.

### **Renal cell carcinoma (RCC) after failure of treatment with sunitinib or sorafenib**

Overall, everolimus is considered to have a positive benefit-risk profile for patients with advanced renal cell carcinoma after treatment failure with sunitinib or sorafenib. The benefits of therapy with everolimus outweigh any potential risks.

### **3 Objectives and endpoints**

Objectives and related endpoints are described in [Table 3-1](#) below.

**Table 3-1 Objectives and related endpoints**

Objective	Endpoint	Analysis
Primary		
To evaluate long term safety data	Frequency and severity of AEs/SAEs	Refer to Section 10.4
Secondary		
To evaluate clinical benefit as assessed by the investigator	Proportion of patients with clinical benefit as assessed by the investigator at scheduled visits	Refer to Section 10.5

## 4 Study design

### 4.1 Description of study design

This is a multi-center, open label study to better characterize the long-term safety of everolimus in patients currently being treated in a Novartis-sponsored OGD&GMA study and who are not progressing on the current study treatment as judged by the investigator. Parent studies eligible to participate in the roll-over study will be decided by Novartis. Investigator initiated trials (IIT) will not be included.

There will be no screening period for this study. Eligible patients can start their treatment with everolimus as soon as they enter the study. All patients must report to the study site for their first visit and commence study participation. At that time, a quarterly supply of everolimus may be dispensed to the patient/or as per local practice.

Patients must return to the study center at least on a quarterly basis ( $\pm$  1 week) for resupply of study medication. Drug dispensing information and adverse events will be collected. The patient may return to the clinic at any given time as per standard of care or treating physician recommendation; however only the quarterly study visits will be recorded. Study medication dispensed will be recorded on the dose administration page.

[figure not shown]
All reported adverse events and serious adverse events will be collected throughout the study.

Patients will continue to be treated in the roll-over protocol until they are no longer benefiting from their everolimus treatment as judged by the investigator (disease progression), they develop unacceptable toxicities, they withdraw consent, they are non-compliant to the protocol, the investigator feels it is no longer in the patient's best interest to continue everolimus therapy or the patient dies, whichever comes first. At every quarterly visit, the investigator is required to confirm that the patient continues to have clinical benefit and may continue receiving study treatment.

A patient will reach the end of study when everolimus treatment is permanently discontinued.

The study is expected to remain open for 10 years or until such time that enrolled patients no longer need treatment with everolimus or are able to obtain commercial supply according to local regulations for their medical condition.

**Figure 4-1 Study design**

\*Note: The starting everolimus (and Sandostatin LAR® Depot, if applicable) dose will be the same as the last dose received in the parent study.

## 4.2 Timing of interim analyses and design adaptations

Not applicable.

## 4.3 Definition of end of study

End of study is defined as either 10 years duration or when all patients on this study have permanently discontinued everolimus treatment and the end of treatment visit has been performed for each patient, whichever comes earlier.

## 4.4 Early study termination

The study is expected to remain open for 10 years or until such time that enrolled patients no longer need treatment with everolimus or are able to obtain commercial supply according to local regulations for their medical condition.

The study can be terminated at any time for any reason by Novartis. Should this be necessary, the prematurely withdrawn patient should be seen as soon as possible. The investigator may be informed of additional procedures to be followed in order to ensure that adequate consideration is given to the protection of the patient's interests. The investigator will be responsible for informing IRBs and/or ECs of the early termination of the trial.

## 5 Population

### 5.1 Patient population

The investigator or designee must ensure that only patients who meet all the following inclusion and none of the exclusion criteria are offered treatment in the study.

### 5.2 Inclusion criteria

Patients eligible for inclusion in this study have to meet **all** of the following criteria:

1. Patient is currently enrolled in a Novartis-sponsored, Oncology Global Development & Global Medical Affairs (OGD&GMA) study receiving everolimus or everolimus plus Sandostatin LAR® Depot and has fulfilled all their requirements in the parent study.
2. Patient is currently benefiting from the treatment with everolimus, as determined by the guidelines of the parent protocol.
3. Patient has demonstrated compliance, as assessed by the investigator, with the parent study protocol requirements.
4. Willingness and ability to comply with scheduled visits and treatment plans.
5. Written informed consent obtained prior to enrolling into the roll-over study.
  - If consent cannot be expressed in writing, it must be formally documented and witnessed, ideally via an independent trusted witness.

### 5.3 Exclusion criteria

Patients eligible for this study must not meet **any** of the following criteria:

1. Patient has been permanently discontinued from everolimus study treatment in the parent study.
2. Patients who are receiving everolimus in combination with unapproved or experimental treatments.
3. Sexually active males, unless they use a condom during intercourse while taking drug and for 8 weeks after stopping study medication. Males also should not father a child in this period. A condom is required to be used also by vasectomized men in order to prevent delivery of the drug via seminal fluid.
4. Pregnant or nursing (lactating) women, where pregnancy is defined as the state of a female after conception and until the termination of gestation, confirmed by a positive hCG laboratory test.
5. Women of child-bearing potential, defined as all women physiologically capable of becoming pregnant, **unless** they are using highly effective methods of contraception during dosing and for 8 weeks after stopping study treatment.
  - Women are considered post-menopausal and not of child-bearing potential if they have had 12 months of natural (spontaneous) amenorrhea with an appropriate clinical profile (e.g. age appropriate, history of vasomotor symptoms) or have had surgical bilateral oophorectomy (with or without hysterectomy) or tubal ligation at least six weeks prior to randomization. In the case of oophorectomy alone, only when the reproductive status of the woman has been confirmed by follow up hormone level assessment is she considered not of child-bearing potential

**Highly effective** contraception methods include:

- Total abstinence: When this is in line with the preferred and usual lifestyle of the subject. [Periodic abstinence (e.g., calendar, ovulation, symptothermal, post-ovulation methods) and withdrawal are not acceptable methods of contraception].
- Female Sterilization: Have had surgical bilateral oophorectomy (with or without hysterectomy) or tubal ligation at least six weeks before taking study treatment. In case of oophorectomy alone, only when the reproductive status of the woman has been confirmed by follow up hormone level assessment.
- Male partner sterilization (at least 6 months prior to enrolling). [For female study subjects, the vasectomized male partner should be the sole partner for that patient]
- Use of oral, injected or implanted hormonal methods of contraception or placement of an intrauterine device (IUD) or intrauterine system (IUS), or other forms of hormonal contraception that have comparable efficacy (failure rate <1%), for example hormone vaginal ring or transdermal hormone contraception.
- In case of use of oral contraception, women should have been stable on the same pill before taking study treatment.

If a study patient becomes pregnant or suspects being pregnant during the study or within 30 days after the final dose of everolimus, the investigator needs to be informed immediately and ongoing study treatment with everolimus has to be stopped immediately.

## 6 Treatment

### 6.1 Study treatment

Study treatment and investigational treatment refer to everolimus.

#### 6.1.1 Dosing regimen

**Table 6-1 Dose and treatment schedule**

Study treatments	Pharmaceutical form and route of administration	Dose	Frequency and/or Regimen
RAD001/everolimus	Tablet for oral use	2.5 – 10 mg/day	Daily

Everolimus will be provided as 2.5 mg, 5 mg or 10 mg tablets. The investigational treatment is to be stored in a secure locked area while under the responsibility of the investigator. Receipt and dispensing of investigational treatment must be recorded by an authorized person at the investigator's site. Everolimus for the roll-over study can be provided as local commercial material or global supply where appropriate.

At the time of transition to the roll-over study, the starting dose of everolimus should be the same as the last dose that was given in the parent study. Dose modification thereafter may be done at the discretion of the investigator based upon what is in the patient's best interest.

Patients will be instructed to take everolimus orally with a glass of water, once daily at the same time each day, either consistently with food or consistently without food. Dietary habits at the time of enrolling in the study from the parent study should be kept as consistent as possible throughout the study. The tablet should be swallowed as a whole and should not be chewed or crushed.

Please refer to the current everolimus IB and [Section 6.3](#) for further important information on potential dosing precautions regarding concomitant medication interaction with cytochrome p450, p-glycoprotein, and CYP3A4 and the recommended dosing guidance.

##### 6.1.1.1 Dosing regimen for combination therapy treatment

The roll-over protocol is designed to provide continued treatment with everolimus monotherapy to patients. If patients are receiving treatment of everolimus in combination with other approved therapies, they can participate in the roll-over study, but it is not intended for combination with unapproved or experimental treatments. Therefore, for patients receiving everolimus in combination with Sandostatin LAR® Depot on the parent protocol, Sandostatin LAR® Depot will continue to be provided by Novartis or by the investigational site considering local regulations. At the time of transition to the roll-over study, the starting dose of Sandostatin LAR® Depot should be the same as the last dose that was given in the parent study.

**Table 6-2 Combination therapy dose and treatment schedule**

Study treatments	Pharmaceutical form and route of administration	Dose	Frequency and/or Regimen
[Redacted content]			

Study treatments	Pharmaceutical form and route of administration	Dose	Frequency and/or Regimen
Sandostatin LAR® (if applicable)	Intramuscular injection	At discretion of treating physician	At discretion of treating physician

### **6.1.2 Ancillary treatments**

Not applicable.

### **6.1.3 Rescue medication**

Not applicable.

### **6.1.4 Guidelines for continuation of treatment**

The starting dose of everolimus should be the same as the last dose that was given in the parent everolimus study. Following the starting dose, patient's may have their dose of everolimus (2.5-10 mg/day) adjusted based on the investigator's judgment of what dose is in the patient's best interest.

### **6.1.5 Treatment duration**

Patients will continue to be treated in the roll-over protocol until they are no longer benefiting from their everolimus treatment as judged by the investigator (disease progression), they develop unacceptable toxicities, they withdraw consent, they are non-compliant to the protocol, the investigator feels it is no longer in the patient's best interest to continue everolimus therapy or the patient dies, whichever comes first. At every quarterly visit the investigator is required to confirm that the patient continues to have clinical benefit and may continue receiving study treatment. A patient will reach the end of the roll-over study when everolimus treatment is permanently discontinued.

The study is expected to remain open for 10 years or until such time that enrolled patients no longer need treatment with everolimus or are able to obtain commercial supply according to local regulations for their medical condition.

## **6.2 Dose escalation guidelines**

Not applicable.

## **6.3 Dose modifications**

### **6.3.1 Dose modification and dose delay**

Patients will begin the roll-over study at the same dose as the last dose administered in the parent protocol. Dose adjustments are permitted to allow the patient to continue the study treatment at the investigator's discretion. Dose modifications may be applied at the investigator's discretion in conjunction with the most current IB.

Everolimus and Sandostatin LAR Depot® dose changes must be recorded on the Dosage Administration Record eCRFs.

### 6.3.2 Follow-up for toxicities

Patients whose treatment is interrupted or permanently discontinued due to an adverse event or clinically significant laboratory value, should be followed up at least once a week (or more frequently if clinically indicated) for 4 weeks, and subsequently at approximately 4-week intervals, until resolution or stabilization of the event, whichever comes first.

Appropriate clinical experts such as ophthalmologist, endocrinologist, dermatologist, psychiatrists etc. should be consulted as deemed necessary. Patients must be followed for adverse events and serious adverse events for 30 days following the last dose of everolimus.

#### 6.3.2.1 Follow up on potential drug-induced liver injury (DILI) cases

Patients with transaminase increase combined with TBIL increase may be indicative of potential DILI, and should be considered as clinically important events.

The threshold for potential DILI may depend on the patient's baseline AST/ALT and TBIL value; patients meeting any of the following criteria will require further follow-up as outlined below:

- For patients with normal ALT and AST and TBIL value at baseline: AST or ALT  $> 3.0 \times$  ULN combined with TBIL  $> 2.0 \times$  ULN
- For patients with elevated AST or ALT or TBIL value at baseline: [AST or ALT  $> 2 \times$  baseline AND  $> 3.0 \times$  ULN] OR [AST or ALT  $> 8.0 \times$  ULN], combined with [TBIL  $> 2 \times$  baseline AND  $> 2.0 \times$  ULN]

Medical review needs to ensure that liver test elevations are not caused by cholestasis, defined as ALP elevation  $> 2.0 \times$  ULN with R value  $< 2$  in patients without bone metastasis, or elevation of ALP liver fraction in patients with bone metastasis.

Note: (The R value is calculated by dividing the ALT by the ALP, using multiples of the ULN for both values. It denotes whether the relative pattern of ALT and/or ALP elevation is due to cholestatic ( $R \leq 2$ ), hepatocellular ( $R \geq 5$ ), or mixed ( $R > 2$  and  $< 5$ ) liver injury).

In the absence of cholestasis, these patients should be immediately discontinued from study drug treatment, and repeat LFT testing as soon as possible, preferably within 48 hours from the awareness of the abnormal results. The evaluation should include laboratory tests, detailed history, physical assessment and the possibility of liver metastasis or new liver lesions, obstructions/compressions, etc.

1. Laboratory tests should include ALT, AST, albumin, creatine kinase, total bilirubin, direct and indirect bilirubin, GGT, prothrombin time (PT)/INR and alkaline phosphatase.
2. A detailed history, including relevant information, such as review of ethanol, concomitant medications, herbal remedies, supplement consumption, history of any pre-existing liver conditions or risk factors, should be collected.
3. Further testing for acute hepatitis A, B, C or E infection and liver imaging (e.g. biliary tract) may be warranted.
4. Obtain PK sample, as close as possible to last dose of study drug, if PK analysis is performed in the study.

5. Additional testing for other hepatotropic viral infection (CMV, EBV or HSV), autoimmune hepatitis or liver biopsy may be considered as clinically indicated or after consultation with specialist/hepatologist.

All cases confirmed on repeat testing meeting the laboratory criteria defined above, with no other alternative cause for LFT abnormalities identified should be considered as “medically significant”, thus, met the definition of SAE ([Section 8.2.1](#)) and reported as SAE using the term “potential drug-induced liver injury”. All events should be followed up with the outcome clearly documented.

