3. Its relationship to the study treatment (reasonable possibility that AE is related: No, Yes)
4. Action taken with respect to study or investigational treatment (none, dose adjusted, temporarily interrupted, permanently discontinued, unknown, not applicable)
5. Whether medication or therapy was given (no concomitant medication/non-drug therapy, concomitant medication/non-drug therapy)
6. Whether it is serious, where a serious adverse event (SAE) is defined as in Section 8.2.1

If the event worsens the event should be reported a second time in the CRF noting the start date when the event worsens in toxicity. For grade 3 and 4 adverse events only, if improvement to a lower grade is determined a new entry for this event should be reported in the CRF noting the start date when the event improved from having been Grade 3 or Grade 4.

All adverse events should be treated appropriately. If a concomitant medication or non-drug therapy is given, this action should be recorded on the Adverse Event CRF.

Once an adverse event is detected, it should be followed until its resolution or until it is judged to be permanent, and assessment should be made at each visit (or more frequently, if necessary) of any changes in severity, the suspected relationship to the study treatment, the interventions required to treat it, and the outcome.

Progression of malignancy (including fatal outcomes), if documented by use of appropriate method (for example, as per RECIST criteria for solid tumors or as per Cheson's guidelines for hematological malignancies), should not be reported as a serious adverse event.

Adverse events separate from the progression of malignancy (example, deep vein thrombosis at the time of progression or hemoptysis concurrent with finding of disease progression) will be reported as per usual guidelines used for such events with proper attribution regarding relatedness to the drug.

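### In bone metastasis, Section 6.3.2.1 lets a raised ALP liver fraction count as cholestasis whatever the R value, so a hepatocellular pattern (R ≥ 5) can escape the immediate stop and early repeat liver test

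*Protocol*

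**What the plan says.** Protocol Section 6.3.2.1 first sets the laboratory trigger. With normal baseline values, it is AST or ALT above 3.0 x ULN together with total bilirubin (TBIL) above 2.0 x ULN. It then asks for a judgement on cause: "Medical review needs to ensure that liver test elevations are not caused by cholestasis".

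The same sentence defines cholestasis in two branches. The first is ALP above 2.0 x ULN with R below 2; the text continues "in patients without bone metastasis, or elevation of ALP liver fraction in patients with bone metastasis". So the ALP limit and the R limit are both written for patients without bone metastasis, and the second branch carries neither.

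The Note that follows defines R as ALT divided by ALP, each in multiples of ULN, and says: "It denotes whether the relative pattern of ALT and/or ALP elevation is due to cholestatic" (R ≤ 2), hepatocellular (R ≥ 5) or mixed injury (R between these). It does not limit these labels by bone-metastasis status.

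The action is conditional: "In the absence of cholestasis, these patients should be immediately discontinued from study drug treatment". The instruction goes on to "repeat LFT testing as soon as possible, preferably within 48 hours from the awareness of the abnormal results".

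**The concern.** The definition and the Note can give opposite answers for the same blood result, and the definition controls the action. A patient with bone metastasis, raised transaminases, raised bilirubin and R of 5 or more has a hepatocellular pattern by the Note. If the ALP liver fraction is also raised, the definition allows the case to be called cholestasis. The stop and the timed repeat test are written only for cases without cholestasis, so they need not follow.

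What is at stake is patient safety: someone with the liver pattern the section is meant to catch could stay on everolimus without an instructed early retest. There is a smaller effect on records. The section's specific serious-event term for drug-induced liver injury (DILI) depends on confirmation by repeat testing. The hepatic listings in SAP Sections 2.8.4 and 2.8.5 are produced only when DILI cases occur.

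**Working it through.** The plan gives no figure to reproduce, so the check is to apply the rule as written.

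**Inputs (Protocol 6.3.2.1)**
- Trigger, normal baseline: ALT or AST > 3.0 and TBIL > 2.0 (x ULN).
- R = (ALT/ULN) / (ALP/ULN).
- Cholestasis without bone metastasis: ALP > 2.0 and R < 2, that is, ALP > max(2.0, ALT/2).
- Cholestasis with bone metastasis: liver fraction raised.

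**Assumed for illustration:** normal baseline, TBIL 2.5 x ULN, liver fraction raised, any elevation counting. All five rows meet the trigger.

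| ALT | Total ALP | R | Pattern by the Note | No bone metastasis | Bone metastasis, as written |
|---|---|---|---|---|---|
| 4 | 2.5 | 1.60 | cholestatic | exempt | exempt |
| 8 | 2.5 | 3.20 | mixed | stop, retest | exempt |
| 10 | 1.5 | 6.67 | hepatocellular | stop, retest | exempt |
| 12 | 2.2 | 5.45 | hepatocellular | stop, retest | exempt |
| 15 | 3.0 | 5.00 | hepatocellular | stop, retest | exempt |

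The last three rows are the conflict. Without bone metastasis, an ALT of 10 is exempt only if ALP exceeds max(2.0, 10/2) = 5.0 x ULN.

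**When the conflict can arise.** R ≥ 5 means total ALP ≤ ALT/5.
- If any liver-fraction elevation counts and total ALP is above 1.0 x ULN, ALT must exceed 5 x 1.0 = 5 x ULN. The upper limit on total ALP is 6/5 = 1.2, 10/5 = 2.0 and 20/5 = 4.0 x ULN at ALT 6, 10 and 20.
- If the 2.0 x ULN limit is read as carrying over to this branch, ALT must exceed 5 x 2.0 = 10 x ULN. The row at ALP 1.5 then drops out; those at 2.2 and 3.0 remain.

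**Can bone ALP explain a high R?** No. Bone ALP adds to the denominator, so it can only lower R. If 0.5 of a total ALP of 1.5 came from bone, R on the rest would be 10/1.0 = 10.0, against 10/1.5 = 6.67 on the total. R ≥ 5 on total ALP therefore cannot be produced by bone ALP.

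**Exposure (SAP 2.1).** The section was added by Amendment 1. At its release 21 patients were ongoing, and 2 consented later: 21 + 2 = 23 of 34. The number with bone metastasis is not given, so the range is 0 to 23.

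**The case against.** The two branches probably differ on purpose. Bone metastasis raises total ALP and lowers R, so R is a poor guide there. That stands for low and middling R. It gives no reason to exempt R ≥ 5, where the distortion runs the other way.

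The operative test is causal and sits with medical review, and the reviewer has the Note in the next lines. The section also requires follow-up of patients over the thresholds, and of all events with the outcome recorded. This stands as a reason why the case may be caught. But the sentence that assigns the review also supplies the definition, and neither follow-up line sets a stop or a date.

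Other safeguards are real but do not close the gap. In Section 6.3.1, "Dose adjustments are permitted to allow the patient to continue the study treatment at the investigator's discretion", which is discretionary. Under Section 6.3.2, patients taken off drug, temporarily or for good, "due to an adverse event or clinically significant laboratory value, should be followed up at least once a week"; a patient kept on drug is not covered. Section 8.1.1 says that "assessment should be made at each visit (or more frequently, if necessary) of any changes in severity", without fixing a time between visits.

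Two stronger readings are tempting and not supported:
- A reader might infer a wait of up to 13 x 7 = 91 days, from the quarterly visit and its one-week window, before the liver is rechecked. Table 7-1 schedules no liver test at any visit, so this would be time to a visit, not to a retest. The triggering result must itself come from testing outside the schedule, and a fractionated ALP suggests that a work-up is already under way. No delay in days can be derived.
- A reader might infer that the primary safety results are compromised. General AE and SAE reporting does not depend on this definition, and no effect on any analysis can be shown.

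**Conclusion.** The gap in the wording is real. As written, a result the section itself labels hepatocellular can be classed as cholestasis when bone metastasis is present, and no other provision overrides that. The consequence is that the stop and the early retest need not follow; the protocol does not forbid either.

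The size is small. The case needs bone metastasis, a raised liver fraction, TBIL above 2 x ULN and total ALP at most one-fifth of ALT. That puts ALT above 5 x ULN, or above 10 x ULN if the ALP limit carries over. The first figure assumes that any elevation of the fraction counts and that total ALP exceeds 1.0 x ULN; the trigger assumes a normal baseline. At most 23 patients were exposed, possibly none with bone metastasis. This is a low-frequency safety wording fix, worth making because the pattern is serious when it occurs.

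**What to change.** In Protocol Section 6.3.2.1, in the bone-metastasis branch, insert after the reference to the ALP liver fraction: *with R value < 5*. Then add to the end of the definition: *; a result with R value ≥ 5 on total ALP is not cholestasis in any patient, and the stop and repeat LFT apply.*

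The cut-off is the Note's own hepatocellular limit. Results with R below 5 in bone metastasis stay with medical review, since bone ALP may be what lowers R. The branches therefore still differ for R from 2 to below 5: ALT 8 with ALP 2.5 (R = 3.2) is stopped without bone metastasis and left to review with it. Requiring R below 2 in both branches would also close the gap, but it would extend the stop to mixed patterns. That is a clinical choice the documents do not settle.

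The cost is a written amendment with the approvals in Section 12.1, late in the study's life, since the June 2020 SAP update already plans the final report. A few patients with R ≥ 5 would be stopped who might have continued. No new visits, scheduled tests or eCRF pages are needed.
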